fMRI Studies: the fMRI activation study will use the Relational and Item Specific Encoding (RISE) task (89,90) to assess brain activation and connectivity patterns underlying item and relational memory. The task, which was developed by the NIMH-funded CNTRACS consortium, is comprised of 3 runs: 1) item and relational encoding; 2) item recognition; and 3) relational recognition. The encode run will comprise presentation of 54 visual object pairs. Pairs will be presented for 4 sec with a variable inter-trial interval of 1-10 sec (4 sec average). Item and relational encoding conditions will be administered in blocks, within a run of 9 trials each. For item encoding, participants will respond via button press yes or no as to whether both objects presented are “living”. During the relational encoding, participants will respond yes or no if one of the objects could fit inside the other. For item recognition participants will view one object from the pairs presented during encoding along with foils. Objects will be presented for 3 seconds with a variable inter-trial interval of 0-10 sec (3 sec average). All objects (108 objects) presented during encoding will be intermixed with 54 foils. Participants will rate their confidence using a 6-point scale as to whether the object is “old” (i.e., previously presented) or “new” (i.e., not previously presented). For relational recognition, participants will view 27 intact pairs intermixed with 27 re-arranged pairs taken from the encoding task. Objects will each be presented for 3 seconds, with a variable inter-trial interval of 0-10 seconds (3 seconds average). Participants will respond “yes” if the pairs were intact from the encoding and “no” if the pair was re-arranged. For resting state fMRI, participants will be given a simple instruction to rest but hold still and keep their eyes open for 15 minutes (allowing for blinks).

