hemodynamic delay. The condition-specific responses will be assessed by performing regression analyses against these functions. Within condition responses, which reflect a condition minus baseline contrast, will be assessed for each of the conditions. Between-condition differences will be assessed by contrasting the task-specific responses with each other. A fixed effects analysis will be performed by entering whole run sequences for all the participants into a single analysis and regressing each sequence against all conditions. Random effects analysis will be used to assess differences between group fMRI data. For this analysis, the contrasts from the first level analysis for each individual will be used to represent mean response patterns for that individual, and between-condition or between-group analyses will be performed. Due to hypothesis regarding anterior cingulated/medial frontal, dorsolateral frontal and hippocampal involvement, between-group differences for BOLD activation within these regions will be examined with an ROI mask approach. In addition, the BOLD signal change will be extracted from these ROIs for each group to examine the hemodynamic time course. In order to obtain the functional connectivity characteristics, we will first manually draw the ROIs for each individual based on anatomic landmarks. Manually traced ROIs nicely overcome the issue of group structural differences. We will use these ROIs to extract the eigenvariates of time series in each participant. The second step will be to elucidate the functional connectivity of each ROIs with the whole brain by a seed-voxel analysis (extracting the weighted mean time series and then entered as covariates in a whole-brain regression analysis). The individual connectivity images created will be taken to a second-level analysis to obtain the connectivity characteristics of these 3 regions at the group level. The next step will be to determine if our a priori ROIs are correlated to each other by calculating the correlations between eigenvariates of each ROI. DMN: For resting state fMRI analysis we will use white matter time course as a regressor, assuming it will contain similar spurious fluctuations as in the gray matter. We will use SPM segmentation module to segment the whole brain white matter. The time course of white matter will be averaged. We will regress out the six head motion parameters and the average white matter time course before cross correlation analysis. Cross correlation maps are then converted to z score maps using an AFNI built-in function. Correlation analyses will be performed by calculating the correlation coefficient between each voxel's time course and the averaging time courses of all the voxels in the defined regions of interest. We will use ROI seed based analyses for all hypothesis testing. Manually traced ROIs overcome the issue of group structural differences. Independent component analysis (ICA), small-world network, SEM, and Granger causality methods can be used to analyze resting state fMRI data. These methods may extract additional circuit information. However, there are still challenges in these methods (113). We will use ICA primarily for extracting the default mode network component for additional exploratory analyses. The Granger causality and small-world brain network methods require some a priori definition of brain regions and the resultant topologic properties of brain networks are highly dependent on the number of brain regions, which remains to be fully evaluated for multiple group x drug comparisons (114,115). A seed-based method is preferred here for testing a priori hypotheses that address specific brain regions. It also takes advantage of this method's higher sensitivity and ease of interpretation (116). 4.4.3.2 MRS: Spectra will be analyzed using the fully automated, standard curve-fitting software, LCModel. Metabolites will be referenced to water and only metabolites of good fits (CRBs< 20) will be included. Voxels will be segmented into CSF, gray, and white matter tissue using SPM8 and in house Matlab code; metabolites will be corrected according to Gasparovic et al. (117). This method produces excellent reliability for glutamate and glutamine as determined by a test-retest reproducibility study in 10 healthy controls scanned twice separated by about 1 week. All spectra were of excellent quality (the average FWHM was 0.021 ppm and the average SNR was 44). Spectral quantification yielded excellent fits as illustrated with Cramer–Rao lower bounds (CRLB) less than 10 for Glu and Glu+Gln and 23 for Gln and test-retest coefficients of variation (CVs) of 9.3 for Gln and 4.2 for

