2): To determine if TRYP-induced elevated KYNA levels alter neural circuit activation and connectivity between the dorsolateral prefrontal cortex (DLPFC) and hippocampus (HPC) during the performance of the Relational and Item-Specific Encoding (RISE; 90) task.

Analysis Plan: In healthy controls and individuals with SRD, we will compare intensity of BOLD signal activation in DLPFC and hippocampus, using the mixed model for repeated measures ANOVA: BOLD activation = treatment + ROI + task condition (item encoding, relational encode, item/relational recall) + treatment x task condition + treatment x ROI + treatment x ROI x task condition + order of treatments + interactions with order, with analyses performed separately in each group. A similar model will be used to examine functional connectivity or correlations between fluctuations in BOLD signal activation between DLPFC and HPC in each task condition, using similar methods previously used to test nicotine challenge effect on resting state functional connectivity (121). To assist in meeting normality assumptions, Fisher's z transformation will be applied to correlation coefficients measuring task-related connectivity prior to modeling.

3): To determine if TRYP-induced elevated KYNA levels alter glutamate levels in the medial (mPFC), a brain region hypothesized to be important in the performance of cognitive tests.

Analysis plan: We will estimate the effect of TRYP or placebo on glutamate in healthy controls or SRD separately and compare whether it is different in these two groups by fitting the mixed model for repeated measures ANOVA: glutamate in mPFC = group + treatment + order + treatment x group + interactions with order, where group indicates healthy controls or individuals with SRD, treatment indicates receiving TRYP or placebo on a given day, and order indicates whether the active treatment is given on the first or second session. In the event of significant interactions between order and treatment, we will examine treatment effects for each order separately; otherwise, order effects will be dropped from the model.

Secondary Aims:

1): To examine if TRYP-induced elevated KYNA levels alter resting patterns of default network activation and connectivity.

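### Primary Aim 2 task connectivity is defined without removing the task-evoked response or forming a separate estimate per encoding condition, so a TRYP effect on activation alone can appear as altered DLPFC-hippocampal connectivity

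*Combined protocol and SAP*

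**What the plan says.** The task-connectivity steps are under Neuroimaging Processing and Analyses, fMRI analyses. ROIs are traced by hand, and then: "We will use these ROIs to extract the eigenvariates of time series in each participant". A seed-to-whole-brain regression follows, and the last step is to "determine if our a priori ROIs are correlated to each other by calculating the correlations between eigenvariates of each ROI".

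In the same section the condition regressors serve to estimate activation: "The condition-specific responses will be assessed by performing regression analyses against these functions". Nothing says that residuals from that fit go on to the connectivity step. The one explicit removal step comes later, in the part on resting data: "We will regress out the six head motion parameters and the average white matter time course before cross correlation analysis".

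Statistical Analysis, Primary Aim 2, makes the outcome "correlations between fluctuations in BOLD signal activation between DLPFC and HPC in each task condition". For the method it points only to a cited challenge study of the resting brain: "using similar methods previously used to test nicotine challenge effect on resting state functional connectivity (121"). On scale, it says that Fisher's z "transformation will be applied to correlation coefficients measuring task-related connectivity prior to modeling". The two groups are analysed separately.

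On the layout of the encoding run, fMRI Studies says: "Item and relational encoding conditions will be administered in blocks, within a run of 9 trials each". Item recognition and relational recognition are separate runs.

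**The concern.** Aim 2 asks two questions about the same regions: does TRYP change activation, and does it change connectivity? During RISE both ROIs are driven by the same stimulus schedule. Unless that shared response is taken out, part of the correlation between the two series is simply the stimulus, and that part grows and shrinks with evoked amplitude. A drug effect on amplitude then moves the correlation even when the underlying coupling is unchanged, and the second answer partly restates the first.

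There is a second gap, which needs no assumption about effect size. The outcome is one correlation per task condition, but item and relational encoding alternate within one run, and the processing section gives no rule for assigning volumes to conditions, no allowance for hemodynamic lag and no condition-interaction model. For the encoding conditions the outcome cannot be computed from the text alone. Both choices could then be made after the results are seen.

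**Working it through.** **The plan's own figure.** Recruitment gives 50 enrolled per group and 10% attrition: 50 × (1 − 0.10) = 45 completers, as stated. The documents give no power, SD or effect size for connectivity, so nothing else can be reproduced.

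**Inputs from the documents.** n = 45 pairs per group; 54 encoding trials of 4 s; intervals of 1-10 s averaging 4 s; blocks of nine, hence 54/9 = 6 blocks; TR 2 s; analysis on Fisher z. A two-sided 0.05 level is stated only for Secondary Aim 2 and is assumed here.

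**Assumptions, not in the documents.** Background correlation ρ = 0.3 under both treatments; between-person SD of z 0.2; session SD of z 0.1; AR(1) coefficient 0.3; evoked share of ROI variance f = 5-30%; TRYP lowers evoked amplitude by 20-50% in both ROIs, or by 30% in one.

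**Size of the shift.** Let background noise have unit variance and the evoked response variance a² in each ROI, so f = a²/(1 + a²). The raw correlation on placebo is (ρ + a²)/(1 + a²). If TRYP multiplies amplitude by m, it becomes (ρ + m²a²)/(1 + m²a²). For f = 0.10 and m = 0.7:

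- a² = 0.10/0.90 = 0.1111; placebo r = 0.4111/1.1111 = 0.370, z = 0.388.
- m²a² = 0.49 × 0.1111 = 0.0544; TRYP r = 0.3544/1.0544 = 0.336, z = 0.350.
- Shift in z: about −0.039, with no change in ρ.

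Simulation gives −0.040 for the whole run and −0.037 within relational-encoding volumes. If the two ROIs respond in opposite directions, the numerator is ρ − a². At f = 0.20 (a² = 0.25), r goes from 0.05/1.25 = 0.040 to (0.3 − 0.1225)/1.1225 = 0.158, a shift of +0.12 in z.

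**False-positive rate.** Simulated encoding runs had 228 volumes, 100 of them in relational encoding after a 4 s lag shift. The test was a paired t-test on Fisher z, n = 45, with 1,000 trials per cell (Monte Carlo SE at most 1.6 points). Order terms and the pooling of conditions in the planned mixed model were left out. Rates for the raw correlation, one condition / whole run:

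| Evoked share | 20% drop, both ROIs | 30% drop, both | 50% drop, both | 30% drop, one ROI |
|---|---|---|---|---|
| 5% | 6% / 9% | 10% / 13% | 13% / 21% | 6% / 8% |
| 10% | 13% / 19% | 21% / 35% | 40% / 66% | 13% / 17% |
| 20% | 35% / 57% | 64% / 86% | 95% / 100% | 31% / 51% |
| 30% | 68% / 90% | 96% / 100% | 100% / 100% | 62% / 84% |

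The one-condition figure is the closer match to the planned outcome. With no amplitude change the raw rate is about 5%. With the condition regressors removed first, rates are 3.3-5.7% over all cells and the mean shift is at most 0.002 in size.

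**Hand check of one cell.** With 100 volumes and AR(1) 0.3 in both series, the effective number is 100 × 0.91/1.09 = 83.5, so the sampling variance of z is 1/80.5 = 0.0124. The SD of the paired difference is √[2 × (0.1² + 0.0124)] = 0.212, and the SE is 0.212/√45 = 0.0316. At f = 20% and a 30% drop the simulated one-condition shift is −0.073; 0.073/0.0316 = 2.31, which gives about 62% rejection against 64% simulated.

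**Sensitivity to noise.** With session SD 0.2 the SE becomes √[2 × (0.04 + 0.0124)]/√45 = 0.048, and the same shift is rejected about 32% of the time. Two further simulations of the 30% drop gave one-condition rates of 7/17/65% and 10/24/39% at shares of 5/10/20%. The rates at 5% and 10% are fairly stable; the rate at 20% is not pinned down.

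**The case against.** The strongest reply is that the plan never says the evoked response stays in. Eigenvariates can be adjusted for task effects when they are extracted, and the text neither states nor excludes this. A reader might infer from the processing section that the response is deliberately kept. The documents do not support that; they are silent, and the word fluctuations in Aim 2 settles nothing. A reader might also infer that a resting-state method is carried over unchanged. The text speaks only of similar methods, without saying which part is borrowed. Both points stand, and they make the finding conditional on the plan being run as written.

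A second reply is that a task-state correlation that includes shared stimulus response is a legitimate description, and that activation is reported beside it. That is fair as far as it goes. But the plan does not define its target as that mixture, and it names connectivity next to activation as something TRYP may alter. If the two are meant to be distinct, the measure should separate them.

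Third, the encoding conditions are blocked and recognition has its own runs, so volumes could be separated. They could, but no rule is given.

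Fourth, the near-nominal error after correction is favourable by construction: the simulated response came from the same regressors that were then removed. This stands as a limit on the remedy.

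**Conclusion.** The concern holds in conditional form. As written, the steps for a Primary Aim 2 outcome neither separate evoked amplitude from coupling nor form a correlation for each encoding condition. A TRYP effect on activation alone can therefore appear as altered connectivity, in either direction.

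The size is an assumption throughout. For amplitude drops of 20-50% in both ROIs, the per-condition false-positive rate is about 6-13%, 13-40% and 35-95% at evoked shares of 5%, 10% and 20%. At the low end this is hardly distinguishable from nominal. Over all cells, including the 30% share and the whole-run correlation, the range is about 6% to 100%.

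Two stronger conclusions are tempting and should not be drawn. One is that a spurious connectivity effect will be reported: that depends on evoked share, on the size and direction of the amplitude change and on session noise, none of which the documents give. The other is to quote the larger whole-run rates as the plan's error rate: Aim 2 specifies a correlation in each condition.

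**What to change.** In Neuroimaging Processing and Analyses and in the Primary Aim 2 analysis plan:

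- State that the condition regressors, together with the motion and white-matter regressors already listed for resting data, are regressed out of each ROI series before any task correlation is computed.
- State that each condition's correlation uses the residuals from that condition's volumes, shifted for hemodynamic lag, and give the shift.
- Name the Fisher z of this correlation as the Aim 2 connectivity outcome.
- Report the raw correlation only as a sensitivity result, beside the activation result for the same ROIs and condition.

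The cost is a change of wording and one regression step on data already planned; no new data are needed. The limit is that any evoked response the model misses stays in the residuals, so the correction is only as good as the fit of the response model. The wording should be settled before anyone sees results by treatment.

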Participants will be recruited from the Maryland Psychiatric Research Center (MPRC) Healthy Control Pool (HP-00042350), MPRC screening protocol (HP-xxxxx) or by advertisements (approved by IRB prior to using). All persons who qualify for this study are referred to the recruiter (PI and/or PI staff) and then contacted and asked if they would like to participate in this study. Interested persons undergo a brief telephone screening followed by an in-person interview. After the initial telephone screen, all potential healthy controls undergo a SCID interview. We will use random digit dialing as our primary source for identifying healthy controls. For random digit dialing, we will utilize contact information lists purchased from Survey Sampling International (SSI), a leading provider of sampling, data collection and data analytic solutions for survey-based research. SSI compiles contact information lists based on census and market-based research data.

Participants with SRDs:

Potential participants with SRDs will be recruited from three sources: the Maryland Psychiatric Research Center (MPRC) clinical programs: the Outpatient Research Program (ORP), the Treatment Research Program (TRP), and the First Episode Clinic (FEC); local outpatient mental health centers; and a standing recruitment database, from which we have enrolled participants in previous MPRC clinical trials.

Potential MPRC and community participants will be identified primarily through chart review or nomination by their primary clinicians who are aware of study entry criteria and demands, and have been asked to identify clinically stable patients who may be interested in research

participation. MPRC and community participants may also be self- or peer-referred for this study.

Healthy controls will be matched to participants with SRDs by age, gender and parental SES level. The planned total enrollment is 50 participants with SRDs and 50 healthy controls, which, under the assumption of 10% attrition, will result in 45 completers in each group. We will enroll 18 participants per year. In each year, we will plan to recruit an equal number of participants with SRDs and healthy controls to avoid potential cohort effects.

Assessments: All of the following assessments will be conducted blind to treatment assignment.

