MRS Study: Glutamate (Glu) and glutamine (Gln; the major metabolite of synaptic glutamate), will be detected in a 4x3x2 cm mPFC voxel using very short TE phase rotation stimulated echo acquisition mode (STEAM: TR/TM/TE= 2000/10/6.5 ms, NEX=256, 2500-Hz spectral width, 2048 complex points, and $\Delta\phi_1 = 135^\circ$, $\Delta\phi_2 = 22.5^\circ$, $\Delta\phi_3 = 112.5^\circ$, and $\Delta\phi_{ADC} = 0^\circ$) (111). We chose the mPFC voxel placement, because previous studies have demonstrated: a) the effect of increased KYNA on glutamate in this region (23); and b) the importance of this region in the performance of cognitive tests (112). Water suppression will be automated using a water suppression enhanced through T1 effects sequence (WET). For measurement of T2*-weighted BOLD effects in whole-brain functional images, we will use echo-planar image (EPI) pulse sequence (TR=2000 ms, TE = 27 ms, flip angle = 80, slice thickness = 4.0 mm, interleaved, and FOV = 220 x 220).

Neuroimaging Processing and Analyses: fMRI analyses: These analyses will be carried out in AFNI, MATLAB, and SPM8. Image preprocessing will include motion correction by coregistration to the first image in each series, correction for differences in slice acquisition times, normalization to a standard Montreal Neurological Institute template, and smoothing by convolution with a Gaussian kernel function (FWHM = 6 mm). Resting state will be low-pass filtered (f cutoff = 0.1 Hz). Task: For the task statistical analysis, for each participant, each of the conditions (item and relational encoding; item and relational recognition) will be modeled as a time series of discrete events that is convolved with a function that accounts for the

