Tryptophan Acquisition and Study Dosing: TRYP is a dietary supplement, whose use is regulated under the FDA Dietary Supplement Health and Education Act of 1994 (DSHEA). We will obtain TRYP powder from Ajinomoto, North American Inc and we have approval under an IND for use in this population. On the morning of the challenge studies, TRYP or placebo (lactose monohydrate) powder will be diluted in water (250 mL) into a slurry immediately prior to oral intake (119). The participant will be instructed to drink the full 250 mL over a one minute time period. The unblinded pharmacist, not participating in assessment procedures, will prepare and dispense the study medications.

Randomization and Blinding:

Treatment assignment (placebo and TRYP) will be randomly assigned, with each participant receiving each condition on separate occasions. Participants will be randomly assigned using a permuted block randomization system with separate randomization sequences for healthy

controls and schizophrenia patients. Treatment assignment order is random within each block, and an equal number of subjects are assigned to each treatment within a block. The block sizes will vary in random sequence and randomization will be matched by age and gender. Thus, it will be difficult to ascertain the next treatment assignment, even if a subject becomes unblinded, while the imbalance of numbers between the treatment groups is kept within tight limits. Randomization requests are sent to the study statistician, who sends a coded treatment assignment to an unblinded pharmacist. Separate emergency unblinding envelopes for each subject will be kept in a locked cabinet at each dispensing pharmacy. All raters, investigators and other staff will be blind to treatment assignment except for the pharmacist. The pharmacist does not participate in study assessments and conveys no information about treatment assignment to subjects or staff except in a medical emergency.

Payment:

Participants will be paid \$15 per hour for each visit (approximately 3 hours for Evaluation and approximately 7 hours for each Challenge visit) as well as \$100 for completion of each Challenge visit. The total payment for the study will be approximately \$455.

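### The Aim 2 BOLD activation model leaves out ROI x task condition, so with categorical factors its treatment x ROI x task test has twice the proper degrees of freedom, and half of them measure differences also present on placebo

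*Combined protocol and SAP*

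**What the plan says.** The Analysis Plan for Primary Aim 2 says "we will compare intensity of BOLD signal activation in DLPFC and hippocampus" with a repeated-measures mixed model fitted separately in healthy controls and in participants with SRD. The model is written term by term. It opens "BOLD activation = treatment + ROI + task condition (item encoding, relational encode, item/relational recall" and continues "treatment x task condition + treatment x ROI + treatment x ROI x task condition + order of treatments + interactions with order".

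Of the three two-way interactions among treatment, ROI and task condition, two are listed. ROI x task condition is not, and no other section supplies it. The order interactions are not itemised. The plan gives no factor coding, software, type of sums of squares or alpha for this model.

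The number of task levels can be read two ways. The Aim 2 list can be taken as three levels, with recall as one. The fMRI analyses text under Neuroimaging Processing and Analyses names four: "each of the conditions (item and relational encoding; item and relational recognition) will be modeled as a time series".

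**The concern.** Treatment x ROI x task condition is the only listed term that asks whether a TRYP effect on activation depends on both region and task condition. For its test to mean that, every lower-order term it contains must already be in the model. If one is left out and the factors are categorical, the three-way term takes over the missing variation.

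The missing variation here has nothing to do with TRYP: it is the extent to which DLPFC and hippocampus differ from one task condition to another, equally on placebo and on TRYP. The documents give no reason to assume that the two regions respond in parallel across encoding and recognition conditions. If they do not, a significant three-way result could not be attributed to TRYP, and this would apply in each of the two groups.

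**Working it through.** The plan gives no df or error rate for this model, so there is no stated figure to reproduce.

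**Inputs from the documents**
- 2 treatments in a crossover (Randomization and Blinding).
- 2 ROIs, DLPFC and hippocampus (Primary Aim 2).
- k = 3 or 4 task conditions (Primary Aim 2; fMRI analyses).
- 45 completers per group: the Recruitment section plans 50, and "under the assumption of 10% attrition, will result in 45 completers in each group"; 50 x 0.9 = 45.

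**Assumptions**
- Alpha 0.05.
- Participant effects with a common within-participant residual SD.
- An ROI x task effect in which one ROI responds more in one condition by δ residual SD, equally on placebo and TRYP. The documents give no BOLD SD or ROI x task effect, so δ is varied from 0.1 to 0.8.

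**Step 1: degrees of freedom.** Cells = 2 x 2 x k. The lower-order terms as listed use 1 (intercept) + 1 (treatment) + 1 (ROI) + (k−1) (task) + (k−1) (treatment x task) + 1 (treatment x ROI) = 4 + 2(k−1). With categorical coding the three-way term takes what remains.

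| | k = 3 | k = 4 |
|---|---|---|
| Cells | 12 | 16 |
| Used by lower terms as listed | 8 | 10 |
| Three-way df as listed | 4 | 6 |
| df belonging to ROI x task | 2 | 3 |
| Three-way df with ROI x task added | 2 | 3 |

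Design-matrix ranks confirm these figures. A formula-based design builder gives separate ROI x task columns for placebo and for TRYP under the three-way label.

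**Step 2: do the order terms rescue it?** The three-way df stay at 4 or 6 with order x treatment alone, with order crossed with the three main effects, and with order also crossed with treatment x task and treatment x ROI. They fall to 2 or 3 only if order x ROI x task is entered.

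**Step 3: false-positive rate when the TRYP effect is exactly zero.** The ROI x task sum of squares for this pattern is δ² x (1 − 1/2) x (1 − 1/k) per participant and treatment. Over 45 participants and 2 treatments the noncentrality is

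λ = 90 x δ² x 0.5 x (1 − 1/k).

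At δ = 0.5:
- k = 3: 90 x 0.25 x 0.5 x 2/3 = 7.5
- k = 4: 90 x 0.25 x 0.5 x 3/4 = 8.44

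Residual df:
- k = 3: 45 x 12 − 45 − 11 = 484
- k = 4: 45 x 16 − 45 − 15 = 660

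The rate is the probability that a noncentral F with (4, 484) or (6, 660) df exceeds its 5% critical value.

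| δ (SD) | λ, k = 3 | Rate, k = 3 | λ, k = 4 | Rate, k = 4 |
|---|---|---|---|---|
| 0 | 0 | 5% | 0 | 5% |
| 0.1 | 0.30 | 6.5% | 0.34 | 6.3% |
| 0.2 | 1.20 | 11.7% | 1.35 | 11.0% |
| 0.3 | 2.70 | 22.0% | 3.04 | 20.6% |
| 0.5 | 7.50 | 56.8% | 8.44 | 55.2% |
| 0.8 | 19.20 | 95.5% | 21.60 | 95.5% |

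With ROI x task condition in the model, λ = 0 and the rate is 5% in every row. Simulation with 4,000 trials per scenario, at 0.2, 0.3, 0.5 and 0.8 SD, gave 12.0, 21.6, 57.6 and 95.8% (k = 3) and 11.8, 20.7, 54.9 and 95.9% (k = 4). With the term added it gave 4.3 to 5.4%.

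**Step 4: reach.** In balanced data, λ from the same ROI x task effect is 0 for the treatment, treatment x task and treatment x ROI tests. The DLPFC-HPC connectivity model has one correlation per task condition and so no ROI factor. The resting-state analysis in Secondary Aim 1 has no task condition. None of these is affected.

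**The case against.** The strongest reply is that the harm needs three things together: the formula is fitted literally, with indicator coding, and without order x ROI x task. The plan states none of these.

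- *Coding.* If the three-way columns are built as products of effect-coded contrasts, the test keeps 2 or 3 df and ROI x task goes into the residual. Simulated rejection is then about 3 to 5%. This stands, but the plan specifies no such coding, and the residual is the wrong place for a systematic effect.
- *Order terms.* An inclusive reading of the order interactions would cover order x ROI x task and restore 2 or 3 df. This also stands, but the term is not named. The only rule stated for order terms belongs to Aim 3: absent a significant order-by-treatment interaction, "otherwise, order effects will be dropped from the model". If that rule were carried over to Aim 2, the term could be dropped again.
- *Shorthand.* Every listed two-way term among the three factors involves treatment, so the omission may be a drafting slip, and standard repeated-measures ANOVA software would normally include ROI x task. That is plausible, but the plan names no software for this model, and the correction is the same either way.
- *Weight.* The three-way term is not named as the primary or gatekeeping test of Aim 2. The terms that bear most directly on whether TRYP alters activation are sound. This limits the point to one test.
- *Size.* The effect sizes, SD unit, error structure and alpha are assumed, so the rates illustrate the problem and do not predict it. The df do not depend on the effect sizes or alpha.

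**Conclusion.** The concern holds. ROI x task condition is absent from a model that is otherwise written out term by term. With categorical factors the treatment x ROI x task test then has 4 or 6 df instead of 2 or 3, and exactly half of them are ROI x task differences that do not depend on TRYP.

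The resulting false-positive rate depends on an ROI x task effect that the documents do not give. It runs from 5% if there is none, through about 12% at 0.2 SD and 55 to 57% at 0.5 SD, to about 95% at 0.8 SD, with 45 completers and an assumed alpha of 0.05. This is conditional on categorical coding and on no order x ROI x task term. Confidence is high in the omission and in the df; the rates are illustrative. It should be fixed, because a literal fit of the listed terms with categorical factors gives a test of the wrong hypothesis within a primary aim.

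**What to change.** Add ROI x task condition to the Aim 2 BOLD activation model, so that treatment, ROI and task condition form a full factorial, and test treatment x ROI x task only in that model. List the order interactions by name, so that the meaning of the three-way test does not depend on how that phrase is read.

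The cost is one model term (2 df with three task conditions, 3 df with four) out of several hundred residual df, plus a line of text. No data collection or study procedure changes.
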